8.4 Warnings and precautions

No evidence available at the time of the approval of this study protocol indicated that special warnings or precautions were appropriate, other than those noted in the product label. Additional safety information will be communicated in the form of Investigator Notifications. This information will be included in the patient informed consent and should be discussed with the patient during the study as needed.

8.5 Data Monitoring Committee

Not applicable.

8.6 Steering Committee

Not applicable.

9 Data collection and management

9.1 Data confidentiality

Information about study subjects will be kept confidential and managed under the applicable laws and regulations. Those regulations require a signed subject authorization informing the subject of the following:

- What protected health information (PHI) will be collected from subjects in this study
- Who will have access to that information and why
- Who will use or disclose that information
- The rights of a research subject to revoke their authorization for use of their PHI.

In the event that a subject revokes authorization to collect or use PHI, the investigator, by regulation, retains the ability to use all information collected prior to the revocation of subject authorization. For subjects that have revoked authorization to collect or use PHI, attempts should be made to obtain permission to collect follow-up safety information (e.g. has the subject experienced any new or worsened AEs) at the end of their scheduled study period.

The data collection system for this study uses built-in security features to encrypt all data for transmission in both directions, preventing unauthorized access to confidential participant information. Access to the system will be controlled by a sequence of individually assigned user identification codes and passwords, made available only to authorized personnel who have completed prerequisite training.

9.2 Site monitoring

Before study initiation, at a site initiation visit or at an investigator's meeting, Novartis personnel (or designated CRO) will review the protocol and CRFs with the investigators and their staff. During the study, the field monitor will visit the site regularly to check the completeness of patient records, the accuracy of entries on the CRFs, the adherence to the protocol to Good Clinical Practice, the progress of enrollment, and to ensure that study treatment is being stored, dispensed, and accounted for according to specifications. Key study personnel must be available to assist the field monitor during these visits.

The investigator must maintain source documents for each patient in the study, consisting of case and visit notes (hospital or clinic medical records) containing demographic and medical information, laboratory data, electrocardiograms, and the results of any other tests or assessments. All information recorded on CRFs must be traceable to source documents in the patient's file. The investigator must also keep the original signed informed consent form (a signed copy is given to the patient).

The investigator must give the monitor access to all relevant source documents to confirm their consistency with the CRF entries. Novartis monitoring standards require full verification for the presence of informed consent, adherence to the inclusion/exclusion criteria and documentation of SAEs. Additional checks of the consistency of the source data with the CRFs are performed according to the study-specific monitoring plan.

9.3 Data collection

The designated investigator staff will enter the data required by the protocol into the Electronic Case Report Forms (eCRF). The eCRFs have been built using fully validated secure web-enabled software that conforms to 21 CFR Part 11 requirements, Investigator site staff will not be given access to the EDC system until they have been trained. Automatic validation programs check for data discrepancies in the eCRFs and, allow modification or verification of the entered data by the investigator staff.

The Principal Investigator is responsible for assuring that the data entered into eCRF is complete, accurate, and that entry and updates are performed in a timely manner.

Safety labs will be collected centrally and data transferred to the study database at regular intervals.

The radiological imaging scans performed for this trial will be submitted by the sites to the CRO (designated by Novartis) to undergo central radiological review. The results of the radiological kidney assessments will be transferred from the CRO to the study database at regular intervals (as agreed upon between Novartis and the designated CRO).

Results from at home pregnancy tests will be recorded in patient diaries for source documentation only.

9.4 Database management and quality control

Novartis personnel will review the data entered by investigational staff for completeness and accuracy. Electronic data queries stating the nature of the problem and requesting clarification will be created for discrepancies and missing values and sent to the investigational site via the EDC system. Designated investigator site staff are required to respond promptly to queries and to make any necessary changes to the data.

Concomitant treatments and prior medications entered into the database will be coded using the WHO Drug Reference List, which employs the Anatomical Therapeutic Chemical classification system. Medical history/current medical conditions and adverse events will be coded using the Medical dictionary for regulatory activities (MedDRA) terminology.

Lab samples (hematology, chemistry, coagulation, serum pregnancy tests) and/or imaging data (kidney CT/MRI scans) will be processed centrally and the results will be sent electronically to Novartis. Digital photographs, brain and chest MRI/CT scans will only be quality checked and archived by the assigned imaging vendor. No central review will take place for the digital photographs, brain, and chest scans.

At the conclusion of the study, the occurrence of any protocol violations will be determined. After these actions have been completed and the data has been verified to be complete and accurate, the database will be declared locked. Authorization is required prior to making any database changes to locked data, by joint written agreement between the Global Head of Biostatistics and Data Management and the Global Head of Clinical Development.

After database lock, the investigator will receive a CD-ROM of the patient data for archiving at the investigational site

10 Statistical methods and data analysis

One safety and efficacy analysis (Final analysis) will be conducted on all patients after they complete their treatment and efficacy follow-up (after 48 weeks of treatment or earlier).

10.1 Analysis sets

10.1.1 Full Analysis Set

The Full Analysis Set (FAS) comprises all patients who received at least one dose of study treatment.

10.1.2 Safety set

The Safety Set comprises all patients who received at least one dose of study treatment. The Safety set and FAS are identical in this study, and will be used for all analysis.

10.1.3 Other analysis sets

Not applicable

10.2 Patient demographics/other characteristics

Demographic and other screening data including disease characteristics will be listed and summarized descriptively using the FAS.

Categorical data will be presented as frequencies and percentages. For continuous data, mean, standard deviation, 25th and 75th percentiles median, minimum, and maximum will be presented.

Relevant medical histories and current medical conditions at screening will be summarized by system organ class and preferred term for all patients.

10.3 Treatments (study treatment, concomitant therapies, compliance)

The Safety set will be used for the analyses below. Categorical data will be summarized as frequencies and percentages. For continuous data, mean, standard deviation, median, 25th and 75th percentiles, minimum, and maximum will be presented.

The duration of exposure in weeks to everolimus as well as the dose intensity (computed as the ratio of actual cumulative dose received and actual duration of exposure) and the relative dose intensity (computed as the ratio of dose intensity and planned dose intensity) will be summarized by means of descriptive statistics.

The number of patients with dose adjustments (reduction, interruption, possible dose re-escalation to starting dose, or permanent discontinuation) and the reasons will be summarized for all patients and all dosing data will be listed.

Concomitant medications and significant non-drug therapies prior to and after the start of the study treatment will be listed and summarized according to the Anatomical Therapeutic Chemical (ATC) classification system for all patients.

10.4 Primary objective

The primary objective in this study is to evaluate the safety of Afinitor[®] in Chinese adults with TSC-renal AML not requiring immediate surgery.

10.4.1 Analysis set and grouping for the analyses

For all safety analyses, the safety set will be used. All listings and tables will be presented for all patients together.

The overall observation period will be divided into three mutually exclusive segments:

1. pre-treatment period: from day of patient's informed consent to the day before first dose of study medication
2. on-treatment period: from day of first dose of study medication to 30 days after last dose of study medication
3. post-treatment period: starting at day 30+1 after last dose of study medication.

10.4.2 Adverse events (AEs)

Summary tables for adverse events (AEs) will include only AEs that started or worsened during the Open-label Treatment phase, the *treatment-emergent* AEs.

The incidence of treatment-emergent adverse events (new or worsening from screening) will be summarized by system organ class and/or preferred term, severity (based on CTCAE version 4.03), type of adverse event, relation to study treatment

Serious adverse events, non-serious adverse events and adverse events of special interest (AESI) during the on-treatment period will be tabulated.

All deaths (on-treatment and post-treatment) will be summarized.

All AEs, deaths and serious adverse events (including those from Screening phase and 30 days safety follow-up visit) will be listed and those collected during the pre-treatment and post-treatment period will be flagged.

10.4.3 Laboratory abnormalities

Grading of laboratory values will be assigned programmatically as per NCI Common Terminology Criteria for Adverse Events (CTCAE) version 4.03. The calculation of CTCAE grades will be based on the observed laboratory values only, clinical assessments will not be taken into account.

CTCAE Grade 0 will be assigned for all non-missing values not graded as 1 or higher. Grade 5 will not be used.

For laboratory tests where grades are not defined by CTCAE v4.03, results will be categorized as low/normal/high based on laboratory normal ranges.

The following summaries will be generated separately for hematology, and biochemistry tests:

- Listing of all laboratory data with values flagged to show the corresponding CTCAE v4.03 grades if applicable and the classifications relative to the laboratory normal ranges

For laboratory tests where grades are defined by CTCAE v4.03

- Worst post- screening CTCAE grade (regardless of the screening status). Each patient will be counted only once for the worst grade observed post-baseline.
- Shift tables using CTCAE v4.03 grades to compare screening to the worst on-treatment value

For laboratory tests where grades are not defined by CTCAE v4.03,

- Shift tables using the low/normal/high/ (low and high) classification to compare screening to the worst on-treatment value.

10.4.4 Other safety data

Vital signs

Data on vital signs will be tabulated and listed, notable values will be flagged.

10.4.4.1 Supportive analyses for primary objective

Not applicable

10.4.4.2 Tolerability

Not applicable

10.5 Secondary objectives

The secondary objectives in this study are to evaluate the efficacy of Afinitor[®] in Chinese adults with TSC-renal AML not requiring immediate surgery with respect to angiomyolipoma response rate, angiomyolipoma progression, and renal function change from screening.

10.5.1 Angiomyolipoma response rate

Angiomyolipoma response rate, is defined as the proportion of patients with an angiomyolipoma response, as defined in [Section 7.2.1.1](#), using data from the Independent Central Radiology Review of CT/MRIs and the Adverse Events CRF page (to identify angiomyolipoma-related bleeding of grade 2 or worse as defined by NCI CTCAE version 4.03).

Angiomyolipoma response rate will be calculated based on the FAS and presented together with its 95% confidence interval for all patients.

10.5.2 Angiomyolipoma progression

Patients with angiomyolipoma progression, as defined in [Section 7.2.1.1](#), will be listed and described in narratives.

10.5.3 Renal function change from screening

Renal function will be assessed using the calculated creatinine clearance (CrCl) from the Cockcroft-Gault formula ([Cockcroft et al 1976](#)). The proportions of patients with severe renal impairment (defined as calculated CrCl < 30 mL/min), and in addition the proportion of patients with NCI CTCAE grade 3/4 serum creatinine will be determined.

10.5.4 Pharmacokinetics

Not applicable

10.5.5 Biomarkers

Not applicable

10.5.6 Resource utilization

Not applicable

10.5.7 Patient-reported outcomes

Not applicable

10.6 Exploratory objectives

Not applicable

10.7 Final analysis

The final analysis will be performed after all patients have completed Week 48 (or discontinued earlier but were followed up for efficacy up to Week 48) and their safety follow-up visit.

10.8 Sample size calculation

Approximately 40 patients will be enrolled to meet the CFDA post approval requirements. The sample size is based on feasibility, there is no hypothesis testing.

10.9 Power for analysis of key secondary variables

Not applicable

11 Ethical considerations and administrative procedures

11.1 Regulatory and ethical compliance

This clinical study was designed, shall be implemented and reported in accordance with the ICH Harmonized Tripartite Guidelines for Good Clinical Practice, with applicable local regulations (including European Directive 2001/20/EC and US Code of Federal Regulations Title 21), and with the ethical principles laid down in the Declaration of Helsinki.

11.2 Responsibilities of the investigator and IRB/IEC/REB

The protocol and the proposed informed consent form must be reviewed and approved by a properly constituted Institutional Review Board/Independent Ethics Committee/Research Ethics Board (IRB/IEC/REB) before study start. Prior to study start, the investigator is required to sign a protocol signature page confirming his/her agreement to conduct the study in accordance with these documents and all of the instructions and procedures found in this

protocol and to give access to all relevant data and records to Novartis monitors, auditors, Novartis Clinical Quality Assurance representatives, designated agents of Novartis, IRBs/IECs/REBs and regulatory authorities as required.

11.3 Informed consent procedures

Eligible patients may only be included in the study after providing written (witnessed, where required by law or regulation), IRB/IEC/REB-approved informed consent

Informed consent must be obtained before conducting any study-specific procedures (i.e. all of the procedures described in the protocol). The process of obtaining informed consent should be documented in the patient source documents. The date when a subject's Informed Consent was actually obtained will be captured in their CRFs.

Novartis will provide to investigators, in a separate document, a proposed informed consent form (ICF) that is considered appropriate for this study and complies with the ICH GCP guideline and regulatory requirements. Any changes to this ICF suggested by the investigator must be agreed to by Novartis before submission to the IRB/IEC/REB, and a copy of the approved version must be provided to the Novartis monitor after IRB/IEC/REB approval.

Women of child bearing potential should be informed that taking the study medication may involve unknown risks to the fetus if pregnancy were to occur during the study and agree that in order to participate in the study they must adhere to the contraception requirement for the duration of the study. If there is any question that the patient will not reliably comply, they should not be entered in the study.

Additional consent form

Not applicable.

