Amendment rationale

At the time of this amendment study enrollment was completed with 40 patients enrolled and treated. Currently all 40 patients are on treatment.

The reason for this protocol amendment is to eliminate the interim analysis.

The intent of the interim analysis was to use the limited available data from CRAD001M2401 for the Chinese Afinitor[®] license renewal package which was planned at the end of 2020. However, due to swift enrollment (12m actual vs 24m planned) the final analysis will be delivered in time to support the Afinitor[®] license renewal for the TSC associated renal AML indication thus eliminating the need for the interim analysis.

The protocol also describes a cut-off date for the interim analysis and a submission date for the Afinitor[®] license renewal, which under new circumstances are not being pursued. Therefore this information will be removed from the protocol.

In addition, some clarifications will be made in the visit evaluation schedule (VES) table and the patient re-screening section.

Major change

1. Elimination of the interim analysis

Minor changes

1. New subject number will be assigned to patients that are re-screened
2. HIV history is sourced documented. Table 7-1 is updated with appropriate category “S”
3. TSC diagnosis has been added to Table 7-1
4. Unscheduled ECGs have been added to Table 7-1
5. The appropriate category “D”, is now assigned to all imaging assessments
6. Protocol reference hyperlinks will be added to the VES Table 7-1 so the reader can link to specific assessments described in Table 7-1
7. Within several sections. Chinese Food and Drug Administration (CFDA) has been replaced with NMPA (National Medical Products Administration), which is the new name for the Chinese Health Authority

Changes to the protocol

Changes to specific sections of the protocol are shown in the track changes version of the protocol using strike through red font for deletions and red underline for insertions.

- Section 4.2 Timing of Interim Analysis: entire section removed describing an interim analysis
- Section 6.4.1 Statement added, “If a patient fails screening and is re-screened a new 7 digit subject number will be assigned”.
- Table 7-1 changes to the VES table include; protocol reference hyperlinks added to each assessment, unscheduled ECGs added, TSC diagnosis added, HIV history data source

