Other tests that will be conducted routinely include laboratory tests for safety, physical examinations, vital signs, and WHO performance status. In addition, for LAM patients, pulmonary function tests will be carried out at 12, 24, 48 weeks, in the open-label treatment phase. Patients with skin lesions will have digital photos of their skin lesions taken at 12, 24, and 48 weeks, in the open-label treatment phase. A complete list of evaluations can be found in [Table 7-1](#). If unforeseen circumstances (i.e., unexpected personal reasons) prevent the patient from complying with the established visit schedule, the site can re-schedule the visit within the prescribed visit window as noted in [Table 7-1](#). The reason(s) for any visit or treatment delays will be documented for the appropriate visit.

All female patients of child bearing potential should perform urine pregnancy tests at home every 4 weeks \pm 7 days from Day 1 to end of treatment (EOT), and enter the result in the pregnancy diary.

Every patient will have end of treatment (EOT) visit within 28 days after last dose. Laboratory tests and imaging will be done at the EOT visit as described in [Table 7-1](#). Laboratory tests that were done within 1 week and imaging that was done within 8 weeks don't have to be repeated at EOT.

All patients will have a safety follow-up visit 30 days after last dose to capture AEs and SAEs that may have occurred after EOT.

Treatment Discontinuation Follow-up phase

Patients without angiomyolipoma progression at the time of early discontinuation of study treatment will enter the Treatment Discontinuation follow-up phase and will be followed with CT/MRI tumor assessments 12, 24 and 48 weeks after Day1, until eventual angiomyolipoma progression, the start of any non-study systemic anti-angiomyolipoma therapy, or withdrawal of consent, whichever occurs first. Patients with SEGA lesions should be followed for routine follow-up with brain MRI/CT scans 12, 24 and 48 weeks after Day1. During this follow up period, the site will continue to send CT/MRIs for central review, and use of non-study systemic anti-angiomyolipoma therapies will be recorded in CRF. Patients with skin lesions will also be followed with digital photography during Treatment Discontinuation follow-up phase.

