4.2 Definition of end of study

The study will end when 40 patients will have completed all scheduled visits as per protocol.

At the end of the study, patients who in the opinion of the Investigator still derive clinical benefit can transfer to prescribed commercial medication. Afinitor[®] is commercially available in China for the studied indication. It is listed on the national reimbursement plan. Patients will need to obtain the medication with a prescription and pay for it per related reimbursement policy after the study ends.

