5.2 Inclusion criteria

Patients eligible for inclusion in this study have to meet **all** of the following criteria:

1. Eligible for treatment with everolimus as per the locally approved label.
2. Presence of at least one AML ≥ 3 cm in its longest diameter using CT or MRI.
3. If female of child bearing potential, documentation of negative pregnancy test at time of Screening. Females of child-bearing potential, defined as all women physiologically capable of becoming pregnant, must use highly effective methods of contraception during dosing and for 8 weeks after stopping medication. Highly effective contraception methods include:
 - Total abstinence: When this is in line with the preferred and usual lifestyle of the subject. [Periodic abstinence (e.g., calendar, ovulation, symptothermal, post-ovulation methods) and withdrawal are not acceptable methods of contraception]
 - Female sterilization: have had surgical bilateral oophorectomy (with or without hysterectomy) or tubal ligation at least six weeks before taking study treatment. In case of oophorectomy alone, only when the reproductive status of the woman has been confirmed by follow up hormone level assessment
 - Male partner sterilization (at least 6 months prior to screening). The vasectomized male partner should be the sole partner for that subject.
 - Use of oral, injected or implanted hormonal methods of contraception or placement of an intrauterine device (IUD) or intrauterine system (IUS), or other forms of hormonal contraception that have comparable efficacy (failure rate $<1\%$), for example hormone vaginal ring or transdermal hormone contraception.

In case of use of oral contraception women should have been stable on the same pill for a minimum of 3 months before taking study treatment

4. Sexually active males must use a condom during intercourse while taking the drug during treatment, and for 8 weeks after stopping treatment. They should not father a child in this period. A condom is required to be used also by vasectomized men as well as during intercourse with a male partner in order to prevent delivery of the drug via semen.
5. Written informed consent according to local guidelines must be obtained prior to any screening procedures.

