7.1.3 Treatment period

Patients will receive the first dose of study drug on Day 1 and continue to be treated per protocol until documentation of angiomyolipoma progression, unacceptable toxicity, pregnancy, withdrawal of consent or investigator decision to stop the study. However, study treatment may prematurely be discontinued for other reasons as well; please refer to [Section 7.1.4](#). The maximum treatment duration is 48 weeks. Patients will visit the investigator site 4, 12, 24, and 48 weeks from Day 1 (± 7 days) and be followed as per the schedule of assessments. At these visits sufficient study drug will be dispensed to the patients to last until the next scheduled visit and unused drug will be returned to the site. Compliance will be assessed by the investigator and/or study personnel at each visit using pill counts and information provided by the patient or caregiver. This information should be captured in the source document at each visit.

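### Protocol 11.3 ties women's contraception to the length of the study, but criterion 3 requires dosing plus 8 weeks; read as own participation, a woman stopping at Week 48 falls 19 to 26 days short

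*Protocol*

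**What the plan says.** Inclusion criterion 3 (Protocol 5.2) sets the rule for women of child-bearing potential: they "must use highly effective methods of contraception during dosing and for 8 weeks after stopping medication".

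Section 11.3 describes what these women should be informed of and agree to. It refers to the contraception requirement but gives it a different end: "in order to participate in the study they must adhere to the contraception requirement for the duration of the study". The 8 weeks are not mentioned there, and the warning about risk to the fetus is likewise limited to pregnancy during the study.

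The length of the study is not defined for this purpose. Section 4.2 gives a trial-level end: "The study will end when 40 patients will have completed all scheduled visits as per protocol". Section 7.2.1, on how long imaging continues after early discontinuation, instead equates end of study with Week 48 for the individual patient.

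Three other statements fix the dates:

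- 7.1.3: "The maximum treatment duration is 48 weeks".
- 4.1: "All patients will have a safety follow-up visit 30 days after last dose". Table 7-1 allows 7 days later.
- 4.2, after the study: "patients who in the opinion of the Investigator still derive clinical benefit can transfer to prescribed commercial medication".

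**The concern.** The protocol gives two periods for one safety obligation. A site that takes its instruction to patients from 11.3 rather than 5.2 could tell a woman that contraception ends with the study. For a woman who has just stopped everolimus, that may fall before the 8 weeks are over.

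The schedule offers little backup. Urine pregnancy tests stop with study drug, and the last serum test is at end of treatment (7.2.2.5.5). The safety follow-up column of Table 7-1 has no pregnancy test. The 24-hour reporting duty in 8.3 is worded for pregnancies that occur on study treatment.

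What is at stake is fetal exposure in a small group of women. No endpoint, analysis set or estimate depends on it.

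**Working it through.** The plan states no figure on this point, so there is none to reproduce. The check is date arithmetic under each meaning of the phrase in 11.3.

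**Inputs**

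- Cover required after the last dose: 8 × 7 = 56 days (5.2, criterion 3).
- Last scheduled contact after the last dose for a patient who completes treatment: Day 30, up to 30 + 7 = Day 37 (4.1, Table 7-1).
- Longest treatment: 48 × 7 = 336 days (7.1.3).
- Early discontinuers without progression are imaged up to Week 48 after Day 1, ± 7 days (4.1, Table 7-1).
- Spread of start dates: at Amendment 2 enrollment was complete and "Currently all 40 patients are on treatment". With treatment capped at 336 days, first doses span at most about 336 days.

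**Meaning A: the woman's own participation**

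For a woman who stops at Week 48 and does not move to commercial drug, shortfall = 56 − day of last contact.

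- Contact on Day 37: 56 − 37 = 19 days (19/56 = 34% of the period).
- Contact on Day 30: 56 − 30 = 26 days (26/56 = 46%).

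A woman who stops early without progression and stays in follow-up to Week 48 is short only if her last dose comes after about Day 336 − 56 = 280 (Week 40). With the visit window this is 329 − 56 = Day 273 to 343 − 56 = Day 287. A woman who stops because of progression does not enter that follow-up. Her last contact is the safety visit, so the 19 to 26 days apply to her whenever she stops.

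Taken literally, a study end at Week 48 would leave a completer with no stated cover after her last dose. That wording in 7.2.1 governs when imaging stops, and a safety contact still follows, so I do not use it to size the gap.

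**Meaning B: the trial-level end in 4.2**

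Assume that the last patient to finish completes treatment and that her safety contact is the trial's last visit.

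- Last finisher: short by 19 to 26 days, as above.
- Any other patient: shortfall = (19 to 26 days) − (days between her last dose and the last finisher's last dose), and none once that difference reaches 0.
- First completer: bound for up to about 336 + 30 = 366 to 336 + 37 = 373 days instead of 56.

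Apart from the last finisher, then, only patients whose last dose falls in the final 19 to 26 days of the span are short, each by less than the last finisher. If last doses were spread evenly (assumption), that is 19/336 = 6% to 26/336 = 8% of the span. If half of them fell in the last quarter (84 days), it would be 0.5 × 19/84 = 11% to 0.5 × 26/84 = 15% of patients. On either pattern most patients are bound for longer than 8 weeks.

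Neither meaning gives 56 days except by chance.

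**The case against.** The strongest reply is that 11.3 sets no rule of its own. It points to the contraception requirement, and the only such requirement for women is criterion 3, which includes the 8 weeks. Investigators sign to follow the whole protocol (11.2), and monitoring verifies adherence to the eligibility criteria in full (9.2). This stands in part: criterion 3 is binding and is not displaced. But the sentence in 11.3 goes on to state its own end point, and someone reading only that section would not learn that the obligation outlasts the last dose.

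The consent form is a separate document and may already say 8 weeks. This stands: nothing here shows that any woman was told the wrong period.

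It would also be too strong to say that an error could not be caught. Every patient has a contact at Day 30 to 37, before Day 56, where the obligation can be raised. A congenital anomaly is a serious adverse event (8.2.1), reportable after 30 days if causality is suspected (8.2.2). What remains is that no pregnancy test is scheduled after EOT.

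Three further inferences are tempting but unsupported:

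- **A headcount.** A reader might apply the percentages above to 40 patients. The documents give neither the enrollment pattern nor the number of women of child-bearing potential who stop drug, and the 40 may include men. Any such count would be an average under an assumed pattern, not an upper limit.
- **A gap for everyone.** A woman who transfers to commercial everolimus has not stopped medication, so the Week 48 gap does not apply to her.
- **A second conflict, for men.** Section 11.3 does not mention men, but criterion 4 covers them: "Sexually active males must use a condom during intercourse while taking the drug during treatment, and for 8 weeks after stopping treatment". Their absence from 11.3 contradicts nothing.

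**Conclusion.** The inconsistency is real and minor. Section 11.3 attaches a period to women's contraception that does not match criterion 3 and that the protocol does not define consistently.

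If the phrase is read as own participation, a woman who stops everolimus at Week 48 and does not move to commercial drug is 19 to 26 days short of the 8 weeks. On the trial-level reading that figure belongs to the last finisher only; a few others may be short by less, and most are bound for longer than needed, which is a burden and not a safety risk.

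Any harm requires that a site or the consent form follows 11.3 instead of 5.2, which the documents do not show. The number of women exposed cannot be derived from them.

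**What to change.** In 11.3, replace the reference to the study's duration with: *during treatment and for 8 weeks after the last dose, as in Section 5.2*. Check that the consent form says the same.

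Rewording alone does not change consent already given, since all 40 patients were enrolled by Amendment 2. Sites should therefore also repeat the 8-week end date to each woman of child-bearing potential who stops drug, at the EOT visit or the 30-day safety contact, which may be by telephone (7.1.6). The SAP (2.7.1) already describes data at database lock, so the reminder belongs to the Amendment 2 stage. After that, the rewording serves any later protocol built on this text.

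The cost is one sentence, one document check, and a reminder at a contact already scheduled. No visit, test or analysis is added.
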